- Study design will be in a prospective cohort trial. The first cohort will be patients who are having a cesarean section with OB/GYNs that prefer using paper bandages in patients with BMI <40 and prophylactic wound vacuum therapy in patients with BMI > or = 40. The second cohort will be patients who are having a cesarean section with OB/GYNs that prefer using Mepilex Border Post-Op Ag regardless of BMI.
- This will be a pilot study as infection rates are low enough that a full study would take several years. However, if difference between methods are large enough then the study would be able to reveal this (see sample size section for details)
- There will be two cohorts:

- 1) Cohort 1 - Normal risk (BMI < 40) – standard dressing (sterile gauze dressing)
High risk (BMI > or = 40) – negative pressure wound therapy / "wound vac"
- 2) Cohort 2 - Normal risk (BMI < 40) – silver impregnated silicone dressing
High risk (BMI > or = 40) – silver impregnated silicone dressing

b. Population

i. Inclusion/Exclusion Criteria [See Human Subjects items to be moved here]

- Inclusion/exclusion criteria: pregnant women who have a cesarean section; as the bandage will be applied when women are no longer pregnant (after fetus is delivered) they will technically not be pregnant at the time of inclusion in the study
- Women will be excluded from the study if their bandage / BMI are not compatible with the cohort scheme noted above (for example if the patient's OB/GYN uses a bandage that is different than a wound vac, paper bandage or Mepilex dressing).
- Specific diagnosis & procedure codes – pregnancy, cesarean section not having other abdominal surgery (example: concomitant hernia repair) except for with concomitant bilateral tubal ligation, which is often done with cesarean sections
- Specific demographic inclusion/exclusion criteria – women of child bearing age having cesarean section at Régions Hospital
- We will compare patients to a database of patients who have asked to be excluded from research, we will exclude patients who requested this. This information is kept in central HealthPartners databases.

ii. Sample size

- Sample size of records to be obtained – enrollment will be 2 years, 1000 women
- Sample size for the main analysis – anticipated follow-up of 75%, which would net 750 women

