- A rationale for selecting the sample size is provided and is summarized as due to a 0.5-3% post-operative infection rate in order to adequately power a study to find a difference – the records to be obtained would include all patient who satisfy the inclusion criteria, approximately 500 per year. Based on this study population and anticipated surgical site infection rate of 0.5% in best case scenario and 3% (both better than the national mean) with a power of 80% and alpha 0.05 we would need a study size of 862. As this is the first study of its kind in the comparison groups it would be clinically salient to find significance or not find it as both results would be clinically helpful in guiding obstetricians.
- Follow-up in the postpartum period is notoriously low, approximately 50%. After cesarean most women tend to at least follow-up for an incision check in the clinics or go to the emergency room and thus it would be reasonable to expect 75% follow-up based on author prior clinical experience.
- Counts of patients expected to be study-eligible are approximately 500 / year based on our standard variation in annual cesarean rates.
- Our two cohorts should be of similar size. Approximately half of the OB's have chosen each closure method as their method of choice. All surgeons have similar obstetric volume and so the total group sizes will likely be similar in size. There are no anticipated changes to the current practice over the next two years.

c. Data collection process

i. Process steps for identification of patients or records

- We will use obstetric logs (paper log), MIDAS (electronic log) and hospital/clinic EMR to identify any women who have a cesarean section at Regions hospital in the date window of interest.
- The PI and co-investigators will review the patient records in the bullet points above for surgical site infection. Currently the Infection Prevention department already does this; the charts of the patients identified will be abstracted. All patients in the study will have their charts abstracted as

well by the PI for suggestion of surgical site infection or for any potential complications related to the surgical site coverings (standard gauze bandage, silver impregnated silicone dressing or negative pressure wound therapy device). Any question will be reviewed by an additional co-investigator obstetrician; if there is a discrepancy then the third co-investigator will make a final determination.

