- Patient's will be informed via standard HealthPartners methods, which includes potential inclusion in research unless they request to be excluded.

Who will provide consent? We will ask for a waiver of informed consent.

How will you ensure that the subject understands the consent? We will apply for a consent waiver. In an opt-out manner if a patient requests to not be included we will respect the patient's privacy in making this decision as part of standard HealthPartners policies.

d. Outcome/endpoint and other variable definitions, and instruments used

Definitions: superficial surgical site infection- defined according to Centers for Disease Control and Prevention criteria as infection involving only the skin or subcutaneous tissue occurring within 30 days of surgery with at least one of the following: 1) purulent drainage from the wound or 2) organism identified by culture or wound deliberately opened by the surgeon. Cellulitis will be evaluated as 1) erythema noted in clinical progress notes with antibiotics administered or 2) diagnosis of cellulitis with antibiotics administered. Our secondary outcome was a composite wound complication, including superficial, deep, or organ-space surgical site infection; wound dehiscence; seroma; or hematoma that occurred within 30 days of surgery. Other secondary outcomes included 30-day readmission, 30-day reoperation, and need for antibiotic treatment for any indication. The chart will be evaluated for nursing or provider notes that indicate problems with the bandage. Chart abstraction will be completed to look for other salient complications or factors that were not predicted. Primary and secondary outcomes will be binary with comments possible. Number of clinical visits for complications, enrollment in home healthcare for wound care and length of hospital visits will be noted.

Chart review form will be electronic, it will have the following elements (there will be 3 charts to protect PHI and to blind the analyst from the intervention), all participants will have a study enrollment number to link the data for appropriate analysis:

First form:

MRN	From EMR
Study enrollment #	From 1-1000

Second form:

Study enrollment #	From 1-1000
Intervention	Binary: cohort 1 vs cohort 2
BMI	BMI rounded to the tenths spot

Third form:

Study enrollment #	From 1-1000
Age	#
Enrolled	Yes / no
Follow-up after discharge from home	Yes / no
Complication noted	Yes / no
Date complication noted	Date

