- Possible biases include that while our study may not be powered to detect a difference, that does not inherently mean that a study does not exist if $p>0.05$. While we may draw conclusion based on this it may be a false negative. Selection bias may occur as our patient population has a tendency to be higher risk in terms of maternal morbidity than in many community hospitals. There may be ascertainment bias by the nursing staff reporting on patient complications and the obstetric team taking care of the patient in the hospital, but after the patient leaves that bias should be significantly decreased as it would take effort from the providers in the clinic to check which study group the patient is in (either accessing data or asking the patient).

5. Setting/Environment/Organizational feasibility

- The study will be conducted at Regions Hospital and otherwise by chart abstraction/review
- Cesarean section are done in the hospital-setting, thus the location is appropriate. We selected Regions Hospital as hospital leadership has already committed to using the incisional coverings despite their costs, thus the study can be completed over a long time course and over an anticipated 1000 patients. Other hospitals have not been systematically willing to use these coverings due to concern for cost; Regions pays for it due to the benefits that we believe have been demonstrated by our organization, which impacts reimbursement and thus this will be overall revenue neutral. Leadership is motivated to have the lowest overall surgical site infection. The Infection Prevention department collects much of the information we are studying and thus with minimal effort the organization will be providing much of the data abstraction.
- The study will fit in with HealthPartners Triple Aim in the following ways. It will improve the health by allowing us to study a change in our practice pattern in a systematic manner and apply the changes to our practice. This will also improve the experience of each new family as complications decrease so the time spent recovering from child birth can be focused on the new family. Finally it will help us improve our fiduciary goals by not just looking at whether infection rates are different but also if there is a significantly different cost-burden with the infections that may be conferred by the different types of incisional coverings.

6. Risks and Benefits

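### The protocol's reassurance about post-discharge ascertainment bias is weaker than stated: the surgeon's identity can reveal the dressing, some infection criteria rest on clinician judgement, and outcome review is not described as masked

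*Combined protocol and SAP*

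**What the plan says.** **Ascertainment.** Section 4.g lists ascertainment bias as a possible bias while the woman is in hospital. It expects much less of it afterwards, because "it would take effort from the providers in the clinic to check which study group the patient is in", either by accessing data or by asking the patient.

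**Cohort.** Section 4.a defines the second cohort as "patients who are having a cesarean section with OB/GYNs that prefer using Mepilex Border Post-Op Ag regardless of BMI". The first cohort is the patients of the other surgeons, with the dressing set by BMI. Section 4.b.ii says about half the surgeons have chosen each method and expects no change over the two years.

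**Outcome.** In Section 4.d a superficial surgical site infection is met by purulent drainage, or by "organism identified by culture or wound deliberately opened by the surgeon". Cellulitis is "erythema noted in clinical progress notes with antibiotics administered" or "diagnosis of cellulitis with antibiotics administered". A separate secondary outcome is "need for antibiotic treatment for any indication".

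**Review.** Under Section 4.c.i the PI abstracts every chart. "Any question will be reviewed by an additional co-investigator obstetrician", and a third co-investigator settles disagreements. Infection Prevention keeps its own register, which is used as a check. The only masking described is of the analyst, through split forms (4.d), yet 4.c.ii has the PI analysing the data as well.

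**The concern.** The reassurance in 4.g treats group membership as something that must be looked up. In this design it is a property of the surgeon. A clinician who knows who operated, and knows that surgeon's habit, can infer the dressing from the BMI. A surgeon seeing her own patient back needs no inference.

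That matters because opening a wound, charting erythema, diagnosing cellulitis and prescribing are all judgements of the treating clinician. Section 3 indicates that the surgeons differ by conviction: some did not want to switch, others switched on grounds of cost. If thresholds for acting differ between the two groups of surgeons, recorded infection rates can differ with no effect of the dressing, or a real difference can be hidden. With single-digit event counts, a few such decisions could shift the comparison that Sections 4.f and 9 say will inform practice. The cost aim is exposed too, since billing data are drawn for women with an identified infection or complication (4.c.i).

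**Working it through.** **Step 1: can the dressing be known after discharge?**

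- Against: all coverings are removed by discharge and wound-care instructions are the same in both groups (4.c.ii, Section 6). The dressing itself is not visible in clinic.
- For: cohort equals surgeon preference (4.a), stable for two years (4.b.ii). Within cohort 1, BMI below or at least 40 determines gauze or negative pressure. Surgeon plus BMI therefore gives the dressing. The surgeons are one group who agreed to the study (4.g), and the operating-room nurse records the dressing (4.c.ii).
- Not stated: who sees the woman after discharge. Section 4.b.ii mentions only clinics and the emergency room.

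**Step 2: which criteria depend on the clinician?**

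| Criterion (4.d) | What it needs |
|---|---|
| Purulent drainage | A sign, as charted |
| Organism on culture | A laboratory result, if a culture was ordered |
| Wound deliberately opened | The surgeon's act; no further sign required as written |
| Cellulitis, route 1 | Charted erythema and antibiotics |
| Cellulitis, route 2 | Diagnosis and antibiotics |

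Antibiotics alone meet no infection definition; they count alone only in the separate secondary outcome. Cellulitis is defined apart from superficial infection and is not named in the secondary composite, although Section 2 counts it among the infections, so its place in the endpoint is unclear.

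**Step 3: confirm the plan's inputs.** For 0.5% versus 3%, two-sided alpha 0.05, power 80%, 1:1, pooled variance and no continuity correction, the sample size is 431 per cohort and 862 in total, matching 4.f.

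**Step 4: expected events.** Section 4.b.ii anticipates 750 women analysed, so about 750 / 2 = 375 per cohort. Section 3 gives a local rate of 0.8 to 2%.

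- 375 × 0.008 = 3.0
- 375 × 0.02 = 7.5

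The smallest splits giving two-sided Fisher p<0.05 at 375 per cohort are 0 v 6, 1 v 8, 2 v 10, 3 v 12 and 4 v 13.

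**Step 5: effect of differential recording.** Let both cohorts have true rate p, and let one be recorded at f × p. Take the two counts as independent Binomial(375, p) and Binomial(375, f × p), and sum the probability of every pair of counts with p<0.05. The values of f are assumptions, and so is 1% as a rate within the local range.

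| True rate | f | Fisher | Chi-squared, uncorrected |
|---|---|---|---|
| 1% | 1 | 1.6% | 4.4% |
| 1% | 1.5 | 4.4% | 8.0% |
| 1% | 2 | 12.2% | 18.0% |
| 2% | 1 | 2.6% | 4.5% |
| 2% | 1.5 | 9.8% | 13.7% |
| 2% | 2 | 29.7% | 36.3% |

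**Step 6: effect on the estimate.** Take 6 true infections in each cohort, and suppose one surgeon group acts half as often on discretionary criteria (assumption). If half the cases are discretionary (assumption), that cohort records 3 + 1.5 = 4.5, a ratio of 4.5 / 6 = 0.75. If all are, it records 3, a ratio of 3 / 6 = 0.5. With no discretionary cases the ratio is 1, and reversing the groups inverts each figure. The 6 v 3 split has Fisher p=0.51.

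**The case against.** The plan acknowledges the bias and claims only that it is reduced. That is fair: a reader might infer that the protocol says clinic staff cannot know the group, and it does not. Nor do the documents support saying that the design gives no protection, or that providers always know. The dressing is gone by the clinic visit, and for an emergency or clinic provider unfamiliar with the surgeon's habit the argument in 4.g holds.

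Infection Prevention reviews independently and is said to detect infections noted outside the system (4.g), which is a real cross-check. But it is not described as masked, and it cannot undo a treating clinician's decision to open a wound or prescribe.

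The magnitude rests on assumed inputs. Even the illustrative 6 v 3 is far from significant, so a reader should not infer that modest differences in threshold would produce a positive result; they would mainly distort the estimate.

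Finally, this is a self-described pilot with non-random cohorts, and surgeon-specific thresholds are one part of a wider confounding by surgeon. That limits how much any single repair can achieve, but it does not support the reassurance as worded.

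A further objection concerns the remedy: masked review after the event addresses the abstractor, not the clinician's threshold. That is correct, and the two problems need separate measures.

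**Conclusion.** The point holds in a limited form. Post-discharge ascertainment bias may persist because cohort can be inferred from the surgeon, some routes to infection depend on the treating clinician's judgement, and neither the abstraction nor the second review, which happens only when a question arises, is described as masked. How often the treating provider knows the dressing cannot be determined from the documents.

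The direction and size of the bias are unknown. A doubled recorded rate in one cohort is a stress test, not an estimate: under it the chance of a spurious Fisher result reaches about 12% at a 1% rate and 30% at 2%. The documents give no ground for saying that either dressing would be favoured, or that bias of this size will occur. The improvement is worth making because it is cheap and needs no change in patient care.

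**What to change.** 1. **Treating clinician's threshold.** Add a form field for the criterion each case met. Section 4.d already provides for complication type, notes and culture data, but not for this. Add a sensitivity analysis limited to purulent drainage or organism on culture. State that it will have few events (1.5 to 3.75 per cohort if half of the 3 to 7.5 qualify, an assumption) and that culture and charting still depend partly on the clinician.
2. **Abstractor bias.** Have every event flagged by the abstractor or on the Infection Prevention register classified by one of the co-investigators already provided for in 4.c.i who did not operate on that patient, from an extract with dressing and surgeon removed.
3. **Wording of 4.g.** State that providers who know the surgeon can be expected to know the dressing, so ascertainment bias may persist after discharge.

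The cost is one form field, one extra table, some redaction work and co-investigator time on flagged charts, with no new staff. The drawback is the small event count in the restricted analysis, which should therefore be reported as counts and an interval alongside the main result, not in place of it.
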